Our objective is to determine the effect of and compare two different doses of IV dexamethasone given preoperatively before TKA, when compared to placebo, using the outcome measures listed below:

Primary Outcome Measures

- To assess patient reported visual analog pain scores.
- To assess patient controlled analgesic usage.

Secondary Outcome Measures

1. To assess the soft tissue swelling about the operative knee after steroid administration.
2. To assess postoperative glucose levels after steroid administration.
3. To assess rehabilitation parameters such as postoperative knee range of motion and time to physical therapy clearance.
4. To assess incidence of nausea and vomiting postoperatively after steroid administration.
5. To assess patient satisfaction and function scores at 4 months with both Short Form (SF) – 12 and Knee Injury and Osteoarthritis Outcome Score Short Form (KOOS, Jr.) scores.
6. To assess hospital admission characteristics such as length of stay and rate of readmission.
7. To assess the risk of infection at 4 months and wound drainage at 7 days after perioperative steroid administration in total knee arthroplasty.

Study Design and Methods

We plan to conduct a prospective, double-blinded, randomized, placebo-controlled trial to evaluate perioperative glucocorticoid administration in total knee arthroplasty. There will be three arms in the study: 1) Placebo, 2) 10 mg dexamethasone, and 3) 20 mg dexamethasone.

Consent to Participation in the Study

Patients will be given the opportunity to participate in the study at the time of consent for surgery and blood product, which typically takes place in clinic during an evaluation for severe end-stage arthritis. It will be emphasized that study participation is optional, and that patients may be randomized to the control or placebo group. Patients will sign the combined informed consent and HIPAA form in order to participate in the study.

Method of Randomization

Once a patient chooses to be part of the study, he/she will be randomized in a blocked fashion to either the control group or to one of two intervention groups. Randomization will occur after informed consent has been obtained from the patients and after the preoperative screening examination is complete. Patients and investigators will be blinded to the randomization assignment. Emory's Investigational Drug Services will randomize each patient prior to dispensing the blinded dexamethasone/placebo doses.

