Therapeutic Intervention

Patients in the intervention arms will receive two doses of either 10 mg dexamethasone or 20 mg dexamethasone. The first dose will be administered preoperatively within three hours of surgery once the patient receives anesthesia. The second dose will be administered eight hours after the first dose in the inpatient setting by the nurse in that unit. The second dose will be administered using a piggyback setup. Patients in the placebo arm will receive two doses of saline/placebo.

This particular dosing is chosen based on available literature that suggests a safe and effective dose is between 4 and 20 mg of dexamethasone²⁵⁻²⁶.

The administration of either steroid or placebo will occur in a double-blinded fashion. For each study participant, two blinded doses will be sent over from Emory's Investigational Drug Service (IDS). Thus, neither the patient receiving the medication nor the health care professional administering the medication or collecting study outcome data will be aware of whether or not the patient received the steroid or the placebo.

Both the intervention and control groups will receive spinal anesthesia using lidocaine and a standard multimodal postoperative pain management regimen typically used for total knee arthroplasty. This regimen will be standardized across all three attending surgeons participating in the study. The standard multimodal pain management regimen will be as follows:

- Preoperative:
 - **Decadron: 10 or 20mg IV x 2 doses, 8 hours apart (if randomized to study group)**
- Intraoperative:
 - **Ropivacaine:** Given intraoperatively. Injection, subcutaneous tissue/skin. Administered in standard fashion. (300mg)
 - **Toradol:** 30mg q 6hr for 6 total doses. 1st dose given intraoperatively at incision. (15 mg if patient is >65 years of age. Patients with Cr >1.5 will not receive Toradol).
- Postoperative
 - **Tylenol:** 1000mg po q 8hr (scheduled)
 - **Oxycodone:** 5mg or 10mg q 3-4hr prn pain, If intolerant to Oxycodone: second agent line is Hydrocodone or Oral Dilaudid (Tylenol will be adjusted accordingly if patient receives Hydrocodone).
 - **IV Morphine (or Dilaudid):** 1 or 2 mg q 2hr prn breakthrough pain
 - **Morphine PCA:** only for failure of the above
 - **MS Contin:** 15 mg BID for two weeks

On postoperative day (POD) 1, patients will be transitioned to oral (PO) and intravenous (IV) medications on an as-needed basis with a regimen that will be standardized across all study participants.

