This study will be conducted at Emory University Orthopaedic and Spine Hospital and Clinic. The investigators perform over 500 total knee arthroplasty procedures per year. We estimate 75% (375) of the patients will be eligible and be willing to participate in the study. The Department of Orthopaedics staff performs 10-20 clinical trials per year and therefore is well-trained and prepared to perform clinical trials of this magnitude.

Inclusion Criteria

1. Patients undergoing primary total joint arthroplasty of the knee
2. Adult patients ages 18-100 years
3. Patients must have smart phone and/or device for app usage

Exclusion Criteria

1. Current chronic steroid use
2. Patients undergoing revision knee surgery
3. Patients ambulating preoperatively with assistive devices
4. Patients with avascular necrosis of the operative knee
5. Patients with a history of an adverse reaction to glucocorticoid steroids
6. Patients unable to provide informed consent
7. Patients with inflammatory arthritis
8. Prisoners
9. Current smokers
10. Patients <18 years of age
11. Any patient with a complicated postoperative course that requires transfer to the Intensive Care Unit (ICU) or to another facility for further management will be removed from the study.
12. Any contraindication that would prevent the patient from being treated with the standard multimodal postoperative pain management regimen
13. History of infection of surgical knee.
14. Patients with diabetes.
15. Patients that have an intolerance to Toradol.
16. Patients that do not have smart phone and/or device for app usage

Statistical Analysis

In order to adequately examine our primary outcome measure of pain reduction, our target sample size was obtained by a power analysis using retrospective data. Assuming a mean difference in the VAS of 1.5 between placebo vs. low dose and 1.5 for low dose vs. high dose (or 3 between placebo and high dose), in order to achieve 90% power, we will need 47 patients per study arm. Thus, the total number of patients enrolled would need to be at least 141. Based upon historical data, we expect it to take 18 months to reach our target N of 141.

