A subject key listing name, medical record number (MRN), age, sex, and study number will be kept in electronic format on a password-protected, encrypted computer, as well as in the research binder stored in a secure locked file cabinet. Data will be collected on paper case report forms (CRFs) and using the smart device application. The CRFs will not have any identifiable subject information, only the study number and subject's initials. Data will be entered into REDCap, a secure, web based application for building and managing online surveys and databases, by a study team member. The database will be made available to all investigators electronically. Data analysis will be performed by the investigators on a password-protected computer.

Each subject's safety will be monitored by his/her physician/investigator as the study procedures are performed and follow-up visits are conducted. Information regarding complications and adverse events will be gathered at each of the study follow-up visits. During administration of the study drug or placebo, all patients will be under close monitoring by the anesthesia and/or nursing staff. Any difference in risk of infection between study groups will be assessed, and this data will be reported to the Emory IRB as necessary. We will also monitor for and report any adverse outcomes and report to the Emory IRB as necessary. Patients will be followed out to one year after surgery to ensure that the intervention is safe. Notification to the Emory IRB will be done according to the IRB's specific procedures.

No patient will be enrolled in the study and have any study-related procedures performed, including completing subject clinical assessments, before an approved Informed Consent Document is signed.

References

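### Exclusion item 11 removes patients from the study for a complicated course after randomisation and first dosing, and nothing says they are kept, followed or counted in their assigned arm

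*Combined protocol and SAP*

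**What the plan says.** **The rule.** Item 11 of the Exclusion Criteria opens "Any patient with a complicated postoperative course that requires transfer", and its operative words are "requires transfer to the Intensive Care Unit (ICU) or to another facility for further management will be removed from the study". The removal is from the study as a whole, not from one endpoint.

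**Order of events.** Under Method of Randomization: "Randomization will occur after informed consent has been obtained from the patients and after the preoperative screening examination is complete". The same section has the pharmacy service randomise before it dispenses. Under Therapeutic Intervention: "The first dose will be administered preoperatively within three hours of surgery once the patient receives anesthesia".

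**Safety aims.** Item 7 of the Secondary Outcome Measures covers infection and wound drainage. The Data Safety and Monitoring Plan adds "Any difference in risk of infection between study groups will be assessed" and "Patients will be followed out to one year after surgery to ensure that the intervention is safe".

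**Collection routes.** Table 1 schedules infection and wound drainage on each inpatient day and at the 1, 4 and 12 month visits. The Data Safety and Monitoring Plan says "Information regarding complications and adverse events will be gathered at each of the study follow-up visits", and also has each subject's physician monitor safety during study procedures, with reporting to the ethics board. Adverse Event Reporting plans a review every six months.

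**Analysis.** Statistical Analysis plans a repeated-measures mixed model for pain, range of motion, function scores and glucose, valid with data missing at random. It defines no analysis population.

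**A separate, narrower rule.** Item 5 of Data Collection leaves patients transferred to subacute rehabilitation out of the length-of-stay analysis. It names no other analysis.

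**The concern.** An eligibility criterion acts before randomisation. Item 11 acts on the postoperative course, and randomisation protects the comparison only if patients stay in it whatever happens after treatment starts. If dexamethasone raises or lowers the chance of a transfer, the patients who remain in each arm are no longer comparable. Even if transfers are equally common in all arms, the serious events of removed patients can go uncounted.

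What is at stake is mainly safety. The Introduction gives fear of infection and poor wound healing as the likely reason surgeons hesitate to use steroids, and the one-year follow-up exists to address safety. A rule that can take out the patients with the worst early course works against that aim. An unsettled rule also leaves the decision on whom to count until after outcomes are known.

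**Working it through.** **1. What happens to a patient who meets item 11**

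| Question | What the protocol says |
|---|---|
| Already randomised? | Yes: randomised before dispensing |
| Already dosed? | Yes, if surgery went as planned; the second dose, eight hours later, may or may not have been given |
| Are infection or drainage recorded before transfer? | Yes: each inpatient day, Table 1 |
| Are earlier pain, range-of-motion, function and glucose data usable? | The mixed model could use them; no text says they are kept |
| Is there a model for infection, opioid use or length of stay? | Not in the mixed-model list |
| Counted in the assigned arm? | Not stated |
| Followed after removal? | Not stated; complications are gathered at study visits, and nothing says a removed patient attends them |

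The gap is therefore in events after removal, and in whether removed patients are counted by arm at all.

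**2. Pain: power**

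The plan's total reproduces: 3 × 47 = 141. The 47 cannot be derived independently, because no SD is given. Back-calculated for a difference of 1.5, two-sided 5% and 90% power:

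SD = 1.5 × √(47/2) / (1.960 + 1.282) = 2.243 (normal approximation; 2.220 by t-test).

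With an assumed 5% removed, n = 47 × 0.95 = 44.65 per arm:

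power = Φ(1.5 / (2.243 × √(2/44.65)) − 1.960) = Φ(1.200) = 88.5% (88.4% by t-test).

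At an assumed 2% removed, power is 89.4%.

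**3. Pain: bias, if removed patients' data were all left out**

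Bias in active minus placebo = D × (f_placebo − f_active), where f is the share removed and D is the mean pain of removed minus retained patients. Assume D = 2 to 3 points.

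- Equal removal of 2%: 0.
- 2% against 5%: 2 × 0.03 = 0.06 to 3 × 0.03 = 0.09 point. The sign depends on which arm loses more. This is 4% to 6% of the planned 1.5.

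**4. Infection**

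Two-sided 95% Clopper-Pearson upper limits for one arm:

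- 0/47: 7.5%
- 0/46: 7.7%
- 1/47 (2.1%): 11.3%

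Losing one patient from the denominator hardly matters. Reporting 0/46 when the full result is 1/47 does.

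With an assumed transfer rate p, and an assumed risk q that a removed patient has an infection that goes unobserved, the expected number missed among 141 is 141pq, and the chance of at least one is 1 − (1 − pq)^141.

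- p = 1%, q = 2%: 0.03 expected; chance 3%.
- p = 2%, q = 5%: 0.14 expected; chance 13%.
- p = 5%, q = 20%: 1.4 expected; chance 76%. This needs both high assumptions at once and is shown only as the edge of the range.

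**5. Length of stay (secondary)**

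Home-only minus all-patient difference (dexamethasone minus placebo) = pC(rC − hC) − pT(rT − hT), where p is the rehabilitation share, r and h are the mean stays of rehabilitation and home patients, and C and T are the placebo and dexamethasone arms. Assume a 10% placebo share, a 2-day home stay and 1 to 2 extra days for rehabilitation patients.

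- Share cut by one third, with redirected patients staying 0 to 0.5 day less than rehabilitation patients: +0.03 to +0.07 day, which understates benefit.
- Share unchanged: 0.
- Share raised by half, with the same extra stay in both arms: 0.10 × 1 − 0.15 × 1 = −0.05, to 0.10 × 2 − 0.15 × 2 = −0.10 day, which overstates benefit.

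**The case against.** **Data before transfer are covered.** Table 1 records infection and drainage on every inpatient day, safety is monitored throughout, adverse events are reviewed every six months, and the mixed model tolerates incomplete records. This stands, and it confines the point to post-removal events and by-arm counting. It does not close the gap: none of these texts mentions removed patients, and reporting an event to the ethics board is not the same as counting it in the randomised comparison.

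**Blinding protects the comparison.** The protocol says that "neither the patient receiving the medication nor the health care professional administering the medication or collecting study outcome data will be aware" of the assignment. So knowledge of the arm should not drive transfers. This stands too. Bias would need an effect of the drug itself on transfer, and the documents give no data on that.

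**Infection is imprecise anyway.** The trial is sized on pain, infection is one of seven secondary items, and an arm with no events still has an upper limit of about 7.5%. This limits the weight of the point. It is no reason to lose the few events that will be seen.

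**The rehabilitation rule is a defensible choice.** A home-discharge analysis avoids placement delay. This is largely right: any effect is small, rests wholly on assumptions and can change sign.

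**Stronger readings that the text does not support.** A reader might infer that data collected before removal are deleted; being taken out of the study does not say that. A reader might infer that early infections go unrecorded; Table 1 shows otherwise. A reader might also infer that all rehabilitation transfers leave the study; item 5 of Data Collection concerns length of stay only, and item 11 reaches such a patient only after a complicated course.

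**Conclusion.** The point holds in this form: item 11 is a post-randomisation removal rule, and the protocol does not say that removed patients' data are kept, that they are counted in their assigned arm, or that they are followed. It should be fixed, chiefly for the between-group infection and one-year safety comparison.

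The size and direction of any bias cannot be found from the documents, and no claim that the rule favours or harms dexamethasone is justified. At modest assumed rates the chance of missing at least one infection is about 3% to 13%; the 76% case should carry no weight. For pain the effect is small on the assumptions shown: about 1.5 points of power at 5% removal, and under 0.1 VAS point of bias at 2% against 5%. The power figure uses a back-calculated SD and a two-group comparison, not the planned repeated-measures model. The length-of-stay matter is minor.

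**What to change.** 1. Move item 11 out of the Exclusion Criteria and reword it so that transfer to ICU or another facility is a recorded event that ends neither follow-up nor analysis. Leave any stopping of study procedures as a separate clinical matter.
2. In Statistical Analysis, state that all randomised patients are analysed by assigned arm and that data collected before transfer are kept.
3. State that infection and other outcomes are sought to 12 months for these patients, as far as obtainable.
4. Report the number of and reasons for transfers by arm.
5. Secondary: stay is already recorded for each patient (Data Collection, item 9), so report it for all patients with discharge destination by arm, alongside the home-discharge-only analysis. Say which rule applies when a complicated course ends in a rehabilitation facility.

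**Cost.** Protocol wording, plus modest effort to obtain data on patients managed elsewhere; readmission is at present recorded only for the study hospital. All-patient length of stay may include some placement delay, which the home-only analysis shows. No extra patients or study procedures are needed.

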7. **Blood Glucose Levels:** The patient's blood glucose level will be recorded once preoperatively at the pre-anesthesia clinic visit several days before surgery, at POD 1 and at each subsequent in-hospital POD using a hemocue. These do not consist of extra blood tests, as blood draws at these time points are considered standard of care. This data is being collected because hyperglycemia is a potential complication of IV steroid use. If patients experience ketoacidosis or hyperglycemia greater than 300, the study drug/placebo will be discontinued.
8. **Functionality scores:** The Short Form (SF) – 12 and Knee Injury and Osteoarthritis Outcome Score Short Form (KOOS, Jr.) questionnaires will be administered to patients at the baseline visit and at each follow up clinic visit. Both of these standardized function questionnaires are well validated and widely accepted in the literature.
9. **Hospital length of stay and readmission:** We will record the length of each patient's hospital stay and any readmission to our hospital for the 12-month duration of study.
10. **Infection:** Patients will have standard follow up clinic appointments at 1 and 4 months after surgery, at which time the clinical presence of possible wound drainage and periprosthetic infection will be evaluated. Patients will be followed up to 1 year after surgery to monitor for latent infections.

Table 1: Outcome measure and data collection schedule

	Pre-operative clinic visit	Each inpatient day	7 day app usage	2 week app usage	1 month clinic visit	4 month clinic visit	12 month clinic visit
Consent, Enrollment, Randomization	X						
Pain assessment	X	X	X		X	X	X
Opioid usage		X					
Pain medication log			X	X			
Knee swelling	X	X			X	X	
Knee ROM	X	X			X	X	X
Physical therapy milestones		X					
Nausea/vomiting		X	X				
Blood glucose	X	X					
Postoperative infection/Wound drainage		X			X	X	X
Length of stay		X					
KOOS, Jr. and SF-12	X				X	X	X

Consent Process

Patients will be asked to participate in the study at a preoperative clinic visit. The risks, benefits and the optional nature of the study will be emphasized. Patients may withdraw from the study at any given time. Consent will be obtained from one or more of the following three people: the attending surgeon, the orthopaedic surgery resident, or the research coordinator.

Participant Selection

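### The 90% power is set at 141 enrolled with no allowance for withdrawal or planned removal, so it has no margin for any loss

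*Combined protocol and SAP*

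**What the plan says.** In the combined protocol and SAP, the Statistical Analysis section says that "in order to achieve 90% power, we will need 47 patients per study arm". It assumes VAS differences of 1.5 points for each adjacent step and 3 points for placebo versus high dose. It concludes that "the total number of patients enrolled would need to be at least 141", and then that "we expect it to take 18 months to reach our target N of 141". The power calculation is attributed to retrospective data, but no standard deviation is printed.

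Two other places provide for loss. Exclusion Criteria item 11 says that patients whose complicated postoperative course requires transfer to intensive care or another facility "will be removed from the study". The Consent Process section says "Patients may withdraw from the study at any given time". Neither gives an expected rate, and no attrition allowance appears anywhere.

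The analysis is a repeated-measures mixed model with pairwise t-tests at each time point up to 12 months, two-sided at 0.05, valid if data are missing at random. No time point is named as primary.

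**The concern.** A power calculation counts patients who contribute the outcome. Here that count is carried over unchanged as the number to enrol, while the same document foresees patients leaving or being removed. Any loss takes the trial below the number on which the 90% rests.

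What is at stake is how a non-significant result is read, above all for the smaller steps (placebo versus low dose, low versus high dose). It would be taken to have 90% power behind it when the true figure is lower by an unstated amount. Item 11 adds a second problem: removal depends on events after randomisation, so it discards information and can differ between arms.

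**Working it through.** **Inputs from the documents (Statistical Analysis section):** 47 per arm, 90% power, adjacent difference 1.5, placebo versus high dose 3, two-sided test, 0.05 level. The 0.05 and the two-sidedness come from the analysis paragraph; the power paragraph states neither.

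**Assumptions, because the documents are silent:** the 90% refers to one 1.5-point pairwise t-test; loss is 5%, 10% or 20%; each loss removes a whole patient, equally across arms.

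**Step 1. The plan's own total.** 3 × 47 = 141. The total reproduces exactly, with nothing added. If 47 is the smallest whole number reaching 90%, the rounding slack is less than one patient per arm.

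**Step 2. Implied SD.** The 47 cannot be reproduced without an SD, so I solved for the SD that gives 90%.

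- Normal approximation: SD = 1.5 × √(47/2) / (1.960 + 1.282) = 7.27 / 3.242 ≈ 2.24.
- Noncentral t: power = P(|T| > t(0.975, 2n − 2)), where T has noncentrality δ = 1.5 / (SD × √(2/n)). At n = 47 the critical value is 1.986, and power is 90.0% when δ = 3.276, so SD ≈ 2.22.

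**Step 3. Power after loss, SD 2.22, n = 47 × (1 − loss).**

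| Loss | n per arm | δ for 1.5 points | Critical t | Power, 1.5 points | Power, 3 points |
|---|---|---|---|---|---|
| 0% | 47 | 3.276 | 1.986 | 90.0% | >99.9% |
| 5% | 44.65 | 3.193 | 1.988 | 88.4% | >99.9% |
| 10% | 42.3 | 3.108 | 1.989 | 86.7% | >99.9% |
| 20% | 37.6 | 2.930 | 1.993 | 82.4% | >99.9% |

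**Step 4. Sensitivity to what the 90% means.** I repeated steps 2 and 3 with other readings, each with its own back-solved SD: normal or t, one-sided, level 0.025 or 0.05/3, the 3-point contrast, and a three-group F-test. For whichever test the 90% describes, power falls to 88.2–88.6% at 5% loss, 86.1–87.1% at 10% and 81.1–83.5% at 20%. The effect of loss thus depends little on the reading.

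The power of a single 1.5-point contrast depends on it heavily. If the 90% came from the three-group F-test (SD about 4.04), a 1.5-point contrast has about 43% power with no loss. If it came from the 3-point contrast (SD about 4.46 by noncentral t), it has about 36%.

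**Step 5. Joint power, conditional on the reading in step 2.** With SD 2.22 and no loss, the chance that both adjacent 1.5-point steps are significant is about 80% (simulation, 200,000 runs).

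**The case against.** Nothing is miscalculated: 3 × 47 is 141. The figure is written as a minimum, and no loss rate is given, so a shortfall is not proved. This stands in part. The next sentence of the plan treats 141 as the target, which removes most of the comfort of a minimum, but the shortfall remains conditional, and at 5% loss it is under 2 points.

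The whole-patient assumption is harsh for early pain. Data Collection item 1 has nursing staff record pain with each set of vital signs in hospital, the app covers only the first seven days, and owning a device is required for entry. The mixed model keeps the scores that a later dropout has already given. This stands: the shortfall is smaller for inpatient pain than for the late visits. It does not help patients removed under item 11, whose earlier scores may go with them.

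One could also enrol more instead of restating the power. To retain 47 per arm at 10% loss needs 47/0.9 = 52.2, so 53 per arm or 159 in total. The Participant Selection section estimates 375 eligible and willing patients a year, so there is room. That is a legitimate choice for the sponsor, but it is not needed to make the statement correct.

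A reader might infer that Table 1 ("Consent, Enrollment, Randomization" at the preoperative clinic visit) contradicts the Method of Randomization section, where the drug service "will randomize each patient prior to dispensing the blinded dexamethasone/placebo doses", and that cancelled operations would use up allocations. The documents do not support this. The text sets a latest time for randomisation, which a preoperative visit can satisfy, and cancelled operations are not mentioned.

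**Conclusion.** The concern holds as a missing allowance. Enrolment equals the number required for 90% power, the plan itself provides for removal and withdrawal, and the stated power therefore has no margin. Under the assumptions listed above, the 1.5-point contrast loses about 1.6 points of power at 5% loss, 3.3 at 10% and 7.6 at 20%. Placebo versus high dose is essentially unaffected.

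Two stronger conclusions are tempting and do not follow. The first is that the trial fails to deliver 90%, or that fewer than 47 per arm will be analysable. No loss rate is given, and without the SD the 90% cannot be confirmed or refuted even at 47. The second is that the 90% is definitely per pairwise contrast, with 80% for both steps. The plan does not say which test was powered, so the 80% may be quoted only as conditional on that reading.

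This should be corrected, but it does not invalidate the design.

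**What to change.** Keep 141 and amend the Statistical Analysis section to:

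- say that 47 per arm means patients contributing primary pain data;
- give the SD from the retrospective data, and name the contrast and the time point to which the 90% applies;
- state an expected loss with its basis, and restate the power at that loss (86.7% at 10%, if the SD is 2.22 and the contrast is the 1.5-point pairwise one).

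Change Exclusion Criteria item 11 so that randomised patients who are transferred stay in the analysis with all data collected, instead of being removed. This concerns retention of data only, not clinical management.

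Cost: protocol wording, a slightly less favourable stated power and a little more analysis work. No extra patients are needed.
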